4.5 Decision for volume expansion

All children receive a 10 ml/kg crystalloid bolus immediately after induction. The need/decision for a fluid bolus will be determined by the anesthesiologist based on clinical judgement. Currently, the anesthesiologist places an arterial line at the beginning of the case and using pulse pressure variability, HR, SBP, MAP, urine output, and blood loss determines whether or not a fluid or blood bolus is appropriate. Data collected from the CardioQ-EDM, CipherOx-CRI, and bedside ultrasound will not be provided to the care team.

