In recent years with continued technological advancements, there has been enthusiasm about less invasive, and in some cases, non-invasive, tools to gauge volume status. Among these, bedside ultrasonography (performed by providers rather than sonographers) is a common tool used to evaluate the inferior vena cava (IVC) collapsibility index (CI) has been shown to be a reliable tool in adults [8]. Another non-invasive device uses a photoplethysmographic probe (CipherOx-CRI) placed on a digit to calculate the compensatory reserve index (CRI), a marker of proximity to hemodynamic collapse [9]. Both IVC CI and CRI have been shown in multiple adult studies to predict the need for volume expansion, but their utility in the pediatric population is unknown.

The goal of this proposed study is to employ the CardioQ-EDM probe to define fluid responders from non-responders among infants undergoing cranial vault reconstruction for craniosynostosis. After defining these two groups in this single arm prospective trial, we will compare the predictive utility of non-invasive devices such as the CipherOx-CRI and IVC CI to currently employed indices (heart rate, systolic blood pressure, urine output and pulse pressure variability) to gauge the need for additional fluid and ongoing resuscitation. If the CipherOx-CRI or IVC CI proved to be as predictive or better at predicting fluid responders, we hope to replace invasive arterial lines with non-invasive tools to guide resuscitation.

We chose this population for several reasons. First, CHCO performs approximately 50-70 of these cases a year making them a relatively accessible group. Second, these children are generally healthy

Protocol #: 18-2513

PI: [name]

Version date: 07/01/2019

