Reporting bias will be minimized by limiting interactions between the study team and OR team. Furthermore, as all children receive a bolus prior to incision, independent of available indices used to assess intravascular volume status, bias should be minimized for this fluid bolus. As these devices are experimental in this patient population, anesthesiologists will be blinded to hemodynamic data generated by the CardioQ-EDM, bedside ultrasound, and CipherOx CRI. If data is needed in an emergent setting, the subject will be excluded from analysis. Although recorded measurements from the Cardio-Q EDM monitor will be visible to the study team, IVC measurements will be stored and calculated post-hoc by a co-investigator blinded to whether or not the subject is or is not fluid responsive. Additionally, a trained statistician not involved in data collection will be paid for analysis. It should also be noted at [name] is a paid officer of CipherOx but will not be involved in the data collection and analysis.

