4.9.2 CardioQ-EDM Contraindications

- Doppler probes (DP240 and I2n) should not be placed in patients under 16 years of age. We will be using the KDP72 probe
- Do not use where nasal injuries are apparent or may have occurred.
- Do not use where nasal polyps exist.
- Do not use where there are circumstances of facial trauma.
- Do not use where there is a risk of brain injury.
- Do not use in patients undergoing intra-aortic balloon pumping.
- Do not use with carcinoma of the pharynx, larynx or esophagus.
- Do not use with aneurysms of the thoracic aorta.
- Do not use with tissue necrosis of the esophagus or nasal passage.
- Do not use in close proximity to laser surgery.
- Do not use in patients with pharyngo-oesophago-gastric pathology and/or severe bleeding diatheses.

5. Specific Aims:

Aim I: Define fluid responders based on aortic ΔV_{peak} : Among infants undergoing cranial vault reconstruction for craniosynostosis, we aim to determine the proportion who respond to clinically administered fluid or blood products defined by pre- and post-fluid challenge EDM $\Delta V_{Peak} >10\%$.

Mock-up Table 1: Demographics of Responders and Non-Responders to Initial 10 mL/kg bolus prior to surgical incision

Variable	Responders	Non-Responders	P-value
Demographics			
Age			
Weight			
Height			
BMI			
Gender			
Ethnicity			
Duration of NPO status			
Associated syndrome			

Legend: BMI, body mass index; npo, nil per os

Aim II: Calculate the PPV, NPV, sensitivity, specificity, and optimal threshold for CRI and collapsibility index as tools to prediction fluid responder

Protocol #: 18-2513

PI: [name]

[figure not shown]
Version date: 07/01/2019

		Fluid Responsive	
		Yes	No
CRI Threshold	+	True Positive	False Positive
	-	False Negative	True Negative

		Fluid Responsive	
		Yes	No
CI Threshold ($\geq 15\%$)	+	True Positive	False Positive
	-	False Negative	True Negative

Performance will also be calculated for heart rate, systolic blood pressure, mean arterial pressure, pulse pressure variability and stroke volume variability. Two separate analyses will be performed – one for the 10 ml/kg protocolized bolus provided immediately after induction and one accounting for all boluses provided.

Mock-up Figure

Mock-up Table 2 – Performance at predicting fluid responsiveness

Variable	Correlation (r)	AUC
IVC CI		
CRI		
SBP		
PPV		
SVV		
MAP		
HR		

Protocol #: 18-2513

PI: [name]

Version date: 07/01/2019

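### Later boluses are triggered by four of the comparator indices while CRI and CI stay hidden, so the all-bolus analysis cannot fairly rank the indices; the ranking should rest on the protocolized bolus

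*Combined protocol and SAP*

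**What the plan says.** Section 4.5 describes two kinds of bolus. The first is universal: "All children receive a 10 ml/kg crystalloid bolus immediately after induction". For later ones, "The need/decision for a fluid bolus will be determined by the anesthesiologist based on clinical judgement", and the inputs are listed: the anesthesiologist, "using pulse pressure variability, HR, SBP, MAP, urine output, and blood loss determines whether or not a fluid or blood bolus is appropriate". The new measurements play no part: "Data collected from the CardioQ-EDM, CipherOx-CRI, and bedside ultrasound will not be provided to the care team".

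In section 5, Aim II evaluates CRI and CI, then adds the comparators: "Performance will also be calculated for heart rate, systolic blood pressure, mean arterial pressure, pulse pressure variability and stroke volume variability". It plans two analyses, "one for the 10 ml/kg protocolized bolus provided immediately after induction and one accounting for all boluses provided", and calls neither primary. Section 4.8 neither separates protocolized from later boluses nor adjusts for how a bolus came to be given.

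Section 4.7 recognises the difference for the first bolus: "as all children receive a bolus prior to incision, independent of available indices used to assess intravascular volume status, bias should be minimized". It says nothing equivalent about later boluses. The background states the intended use: "If the CipherOx-CRI or IVC CI proved to be as predictive or better at predicting fluid responders", the investigators hope to replace arterial lines.

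**The concern.** Responder status is defined from a pre-bolus and a post-bolus reading (section 4.4), so a moment without a bolus yields no outcome. After the first bolus, moments enter the data partly because PPV, HR, SBP or MAP looked abnormal. Moments when those indices looked reassuring are under-represented. That cuts the range of the triggering indices directly and the range of CRI and CI only through their correlation with them. An index loses apparent discrimination when the sample is selected on it, and it loses more than an equally good index that nobody saw.

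Pooling adds a second distortion. The later boluses have higher values of the triggering indices because of the selection, and section 3 (hypothesis Ib) expects them to have a higher response rate. A pooled AUC then reflects partly which kind of bolus an observation came from, and not only how well an index separates responders within one setting.

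At stake is the comparison of CRI and CI with the arterial-line indices. If it is read from the all-bolus analysis, the ranking and the AUCs themselves depend on clinician behaviour and on the number of later boluses per child.

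**Working it through.** The plan gives no figure for this point to reproduce. The check sets the sections side by side and then uses simulation to see how large the effect could be.

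**Which indices select later boluses**
- Listed triggers (4.5): PPV, HR, SBP, MAP, urine output, blood loss, combined by judgement.
- Comparators (Aim II): HR, SBP, MAP, PPV, SVV.
- Overlap: PPV, HR, SBP and MAP, four of five. SVV is not a listed trigger.
- Hidden: CRI, CI, esophageal Doppler.

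**Model.** A latent normal state defines response, with 50% responding at the first bolus (hypothesis Ia: about half). A new index and a comparator are noisy readings of that state. A later bolus is given when the comparator, alone or with equal-variance other information, is in its top half or top quarter. Assumptions not in the documents: the true AUCs, the selection strength, the number of later boluses per first bolus (1 or 3), and an intra-operative rise in responsiveness (0 or 0.5 SD).

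**Later boluses only, both true AUCs 0.80 (new against comparator)**
- Comparator decides alone, top half: 0.777 against 0.696, gap 0.081.
- Comparator decides alone, top quarter: 0.788 against 0.662, gap 0.126.
- Other information has equal weight, top half: 0.791 against 0.766, gap 0.025.
- Other information has equal weight, top quarter: 0.794 against 0.764, gap 0.030.
- Unselected first bolus: 0.80 against 0.80, no gap.

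**All boluses pooled, both true AUCs 0.80, comparator decides alone**

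| Selection | Rise in responsiveness | Later per first | New | Comparator | Gap |
|---|---|---|---|---|---|
| Top half | 0 | 1 | 0.795 | 0.778 | +0.017 |
| Top half | 0 | 3 | 0.788 | 0.748 | +0.040 |
| Top quarter | 0 | 1 | 0.809 | 0.812 | -0.003 |
| Top quarter | 0 | 3 | 0.805 | 0.774 | +0.031 |
| Top half | 0.5 SD | 1 | 0.823 | 0.840 | -0.017 |
| Top half | 0.5 SD | 3 | 0.822 | 0.816 | +0.006 |
| Top quarter | 0.5 SD | 1 | 0.842 | 0.883 | -0.041 |

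**Why the sign moves.** A pooled AUC averages over responder/non-responder pairs. Take one later bolus per first bolus, response 0.50 at the first and 0.72 at later ones (the simulated rate for top-half selection). The pair total is (0.50 + 0.72) × (0.50 + 0.28) = 0.952, made up of:
- within first: 0.50 × 0.50 = 0.250 (26%);
- within later: 0.72 × 0.28 = 0.202 (21%);
- later responder against first non-responder: 0.72 × 0.50 = 0.360 (38%);
- first responder against later non-responder: 0.50 × 0.28 = 0.140 (15%).

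The range restriction acts in only 21% of pairs. The third group flatters the comparator, because selection made its later values high; the fourth penalises it. With top-quarter selection (later response 0.84), these two groups become 0.420 and 0.080 of 1.34 × 0.66 = 0.884, or 47% and 9%, and the pooled gap all but disappears.

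**When the comparator is truly better (0.80 against 0.75 for the new index), no rise in responsiveness, top half**
- Comparator decides alone: later boluses reverse the order (new 0.730, comparator 0.694). Pooled, three later per first is nearly a tie (0.740 against 0.747); one later per first keeps the order (0.746 against 0.778).
- Other information has equal weight: no reversal in later boluses (0.741 against 0.767).

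**Other settings.** With true AUCs of 0.78 or 0.83, a separate run gave later-bolus gaps of 0.02 to 0.10 and pooled gaps of about -0.02 to +0.03, and moved a true 0.83 to between 0.77 and 0.91. With six equally weighted triggers, later-bolus gaps were +0.024 to +0.070; pooled gaps were -0.009 to +0.008 (one later bolus) and -0.006 to +0.020 (three).

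**The case against.** The strongest reply is that the protocol already plans the clean analysis. The first bolus goes to every child, is analysed separately under Aims II and III, and section 4.7 explains why it is less open to bias. No later-bolus-only analysis is planned, so the largest gaps belong to a set the plan never reports alone. Urine output, blood loss and judgement dilute the selection. The background speaks of a hope, section 2 foresees further studies in other groups, and the available text states no formal test or margin for comparing AUCs.

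Sampling error is also large. Section 4.2 lists 30 probes, each for a single patient (4.9.1). If 30 children split 15/15 and the AUC is 0.80, the Hanley-McNeil variance is [0.16 + 14 × (0.667 - 0.64) + 14 × (0.711 - 0.64)] / 225 = 0.0068, a standard error of about 0.08. That exceeds most of the pooled distortions above.

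Much of this stands, and it rules out a stronger reading. A reader might infer that the all-bolus comparison always handicaps the comparators and so pushes toward dropping arterial lines. The documents do not support that: pooling includes the unselected bolus, and the sign depends on quantities the available text does not give. A reader might also infer that children with reassuring values never enter the study. Every child enters through the first bolus; only later moments are selected.

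What does not stand is that the matter is therefore settled. Planning a clean analysis beside a distorted one, without saying which carries the comparison, leaves the choice open until results are known. Sampling error does not excuse a systematic distortion that more boluses would not remove.

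**Conclusion.** The concern holds in a limited form. Within later boluses, the four triggering comparators lose AUC relative to an equally accurate hidden index, by about 0.02 to 0.10 under the assumed selection strengths. The 0.126 case needs one index to decide alone with only its top quarter treated, which is stricter than section 4.5 describes. In the planned all-bolus analysis both the AUCs and the ranking are distorted, but the direction is uncertain: pooled gaps between equally accurate indices were about -0.02 to +0.03 in one set of assumptions and -0.041 to +0.040 in the harsher one. A near-tie that hides a truly better comparator is possible, not inevitable. These sizes rest on assumed accuracies, selection strength, later boluses per child and intra-operative responsiveness, so they show what is possible and do not estimate what will occur. The qualitative finding rests only on sections 4.5, 4.7, 4.8 and Aim II.

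**What to change.** In section 5, Aim II, with a matching line in section 4.8:

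1. Name the protocolized-bolus analysis as the basis for comparing CRI or CI with PPV, SVV, HR, SBP and MAP, and for any inference about replacing arterial lines.
2. Report later boluses as a separate, clinician-selected stratum, and do not rely on a single pooled AUC.
3. State that rankings in the later stratum are affected by selection on PPV, HR, SBP and MAP, and that SVV is not a listed trigger.

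This takes a few sentences and needs no new data and no change to care. There are two costs. The ranking uses one observation per child, so it gains no precision from later boluses. It also applies only before incision, so the claim for bleeding children, the setting the background most wants to reach, becomes narrower. Later-bolus results can still describe performance there, with the selection stated as a limitation.

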4.6 Data Acquisition

If consent is obtained, a CardioQ-EDM probe will be placed on the day of surgery after induction of general anesthesia. One of the investigators will be present in the operating room for the duration of surgery to perform study procedures (PI or Co-investigators (Drs. [name] or [name]) to place all CardioQ-EDM probes) and gather study data. The anesthesiologist will inform the investigator of plans to provide a fluid or blood bolus per clinical judgement in addition to the protocolized 10 ml/kg bolus provided after induction. While the anesthesiologist is preparing to administer volume expansion, a co-investigator will collect pre-fluid bolus data. Administration of fluid will not be delayed for any reason, including performance of study measurements. Measurements will be recorded for data analysis at the completion of the trial (see below). Additionally, a CipherOx-CRI probe will be placed on the patient's index finger (again, recorded data will be interpreted post hoc) and a bedside ultrasound will be performed by either the PI or one of two co-investigators to measure the IVC CI. The IVC CI will be visualized through a sub-xiphoid window. The ultrasound

Protocol #: 18-2513

PI: [name]

Version date: 07/01/2019

indicator will be aimed at the child's left flank. Once the right atrium is identified, the ultrasound probe will be turned 90 degrees counterclockwise so the indicator is directed at the head. The best way to evaluate the IVC diameter through the respiratory cycle is to use M mode. After positioning the probe appropriately in order to visualize the IVC 2 cm inferior to the cavo-atrial junction, the M mode will be activated to measure variation in the IVC diameter with respiration. Ultrasound cine-loops will be recorded, and CI will be calculated post-hoc. Data will be recorded on the *Data Collection Form* for each fluid bolus administered. The PI and co-investigators will manage all aspects of investigational devices.

Day of Surgery Step-by-step Description:

1. While the anesthesiologist intubates and places an arterial-line, the CardioQ-EDM monitor, CipherOx-CRI device, and U/S will be set up
2. After positioning the patient for surgery, the CardioQ-EDM device will be placed through the mouth into the esophagus by the PI or Co-investigators (Drs. [name] or [name]) and the aortic Doppler waveform will be confirmed. Additionally, the CipherOx-CRI finger probe will be placed, and a baseline IVC CI will be measured and recorded.
3. Baseline values and measurements (included in **Table 3**) will be recorded. Additionally, the baseline ΔV_{Peak} and CRI will be recorded.
4. A protocolized 10 mg/kg crystalloid fluid bolus will be administered
5. Two minutes after the bolus has completed, repeat EDM and CRI values will be recordings and a repeat abdominal ultrasound to measure the IVC CI will be obtained.
6. If an additional fluid bolus or blood transfusion is administered during the remainder of the procedure, steps 3 and 5 will be repeated.

4.6.1 Demographic Data: Age, weight, height, body mass index (BMI), gender, and ethnicity will be collected from medical records.

4.6.2 Ventilator Data: pressure or volume control, tidal volume (ml/kg) and peak end-expiratory pressure (PEEP), peak inspiratory pressure (PIP), and spontaneously breathing.

4.6.3 CardioQ-EDM Data: Based on a validated internal nomogram derived from the child's age, height, and weight[27], peak velocities will be obtained from the Cardio-EDM monitor.

4.6.4 Fluid Data/Vasopressor Administration: Number, time, type, and volume of fluid/blood administered will be recorded in real time. Vasopressor agent, dose, and time administered will also be reported.

4.6.5 Waveform/Vital Data: As it is currently not possible to extract waveform data from the operating room monitors, we will record data in real time. Values listed below will be reported on an excel spreadsheet.

Parameters to measure:

All parameters will be measured x 3 with 30 seconds between each measurement and averaged

- Systolic blood pressure (measured by arterial line)
- Mean arterial pressure (calculated from arterial line)
- Heart rate
- Pulse pressure variability (measured by arterial line) = acquired from arterial line
- Stroke volume variability – acquired from arterial line
- $\Delta V_{peak} = (V_{Peakmax} - V_{Peakmin}) / [(V_{peakmean}] \times 100$
- Compensatory reserve index – algorithmically generated
- Inferior vena cava collapsibility index = Maximum diameter (expiration) – minimum diameter (inspiration)/maximum diameter (expiration) in M mode

4.7 Data Blinding:

Reporting bias will be minimized by limiting interactions between the study team and OR team. Furthermore, as all children receive a bolus prior to incision, independent of available indices used to assess intravascular volume status, bias should be minimized for this fluid bolus. As these devices are experimental in this patient population, anesthesiologists will be blinded to hemodynamic data generated by the CardioQ-EDM, bedside ultrasound, and CipherOx CRI. If data is needed in an emergent setting, the subject will be excluded from analysis. Although recorded measurements from the Cardio-Q EDM monitor will be visible to the study team, IVC measurements will be stored and calculated post-hoc by a co-investigator blinded to whether or not the subject is or is not fluid responsive. Additionally, a trained statistician not involved in data collection will be paid for analysis. It should also be noted at [name] is a paid officer of CipherOx but will not be involved in the data collection and analysis.

